### Observation period

The period of safety observation starts from the time when the patient gives informed consent and is divided into the following periods:

- The PRE-TREATMENT period: defined as the time from the signed informed consent date up to the time of first dose of alirocumab in the OLE study. The adverse events occurring during this period were to be reported and recorded in the parent study database. However, after the lock of parent study database, some exceptional pre-treatment adverse events have been recorded in the OLE study database with a start date in the parent study period.
- The treatment-emergent adverse event (TEAE) period: defined as the time from the first dose of alirocumab in the OLE study up to the day of last dose of alirocumab received in the OLE study + 70 days (10 weeks), as residual effect of alirocumab is expected until 10 weeks after the stop of alirocumab.

The TEAE period will include:

- The TREATMENT period defined as the time from the first dose of alirocumab in the OLE study up to the day of last dose of alirocumab received in the OLE study + 21 days.
- The POST-TREATMENT period: defined as the time starting the day after the end of TEAE period up to the end of study

The on-study observation period is defined as the time from first dose of alirocumab in the OLE study until the last protocol planned visit of the patient in the OLE study. The last protocol planned visit is defined as the safety follow-up call if done, else 10 weeks after last injection of alirocumab.

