# 2.3.1 Efficacy population

The efficacy population considered for efficacy analyses will be the mITT population.

The mITT population is defined as all patients who took at least one dose or part of a dose of the open-label IMP injection and with both of the following conditions met:

- Availability of a baseline (from parent study) calculated LDL-C
- Availability of at least one calculated LDL-C during the efficacy treatment period in one of the analysis windows from Week 8 onwards.

The efficacy treatment period is defined as the time period from the first open-label IMP injection up to the day of last injection +21 days.

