# 3 INTERIM ANALYSIS

Interim analyses may be performed before the end of the study if requested by Health Authorities or if needed for the purpose of scientific communication.

Analyses methods and conventions described in the other sections of this SAP will be applied for all analyses as applicable. The following additional rules will apply for analyses performed at interim analysis:

- Patients without end of treatment visit performed at the time of the cut-off date will be considered as ongoing and exposed up to the cut-off date. Therefore:
  - Patients who did not complete treatment period nor prematurely discontinued the study treatment at cut-off date will be analyzed as "ongoing" in the disposition summary.
  - Their TEAE period, treatment period, efficacy treatment period and on-study observation period will end at the cut-off date.
  - Their treatment duration will be derived by considering date of cut-off as last injection date.
- Analyses of number of injections, mean injection frequency, percentage of days with under/above-planned dosing and compliance will be performed up to the last injection reported in the e-CRF up to the cut-off date.
- AEs occurring, worsening or becoming serious after the cut-off date will not be included in the analyses. However, any available outcome before database lock, regardless of timing in relation to the cut-off date, of an adverse event starting prior to the cut-off date will be taken into account. Medications, treatment discontinuations/completions and deaths occurring after the cut-off date will not be included in the analyses.
- Post-treatment period, post-study period are not applicable for ongoing patients. Analyses
  of post-treatment AEs, post-study deaths and post-treatment medications will be performed
  for patients who either completed or prematurely discontinued the treatment before or at
  the cut-off date.
- Analysis of proportion of patients with insufficient follow-up will be provided for patients
  who either completed or prematurely discontinued the treatment before or at the cut-off
  date.

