# 4 DATABASE LOCK

The database is planned to be locked approximately 4 weeks after common cut-off date (for interim analysis) or last patient last visit (for final analysis).

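### At an interim analysis, patients who have already stopped treatment keep TEAE time after the cut-off in which no adverse event can be counted

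*SAP*

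**What the plan says.** SAP section 3 allows an optional interim analysis, for Health Authority requests or scientific communication, and carries over the SAP's other conventions where applicable. It then adds rules for the cut-off:

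- **Who is ongoing.** The lead sentence reads "Patients without end of treatment visit performed at the time of the cut-off date will be considered as ongoing and exposed" up to the cut-off. A sub-bullet then says "Patients who did not complete treatment period nor prematurely discontinued the study treatment at cut-off date will be analyzed as" ongoing in the disposition summary.
- **Periods of ongoing patients.** "Their TEAE period, treatment period, efficacy treatment period and on-study observation period will end at the cut-off date".
- **Duration of ongoing patients.** "Their treatment duration will be derived by considering date of cut-off as last injection date".
- **Adverse events.** "AEs occurring, worsening or becoming serious after the cut-off date will not be included in the analyses". This bullet is not limited to ongoing patients.

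For patients who have stopped, the general definitions are left in force. The TEAE period in SAP 2.1.4 (Observation period) runs "up to the day of last dose of alirocumab received in the OLE study + 70 days (10 weeks"). The efficacy treatment period in SAP 2.3.1 runs "from the first open-label IMP injection up to the day of last injection +21 days", and the treatment period in 2.1.4 uses the same 21 days. SAP 2.4.5.1 counts patient-years to the first event or, without an event, over the whole TEAE period. It also censors event-free patients at the end of the TEAE period in the Kaplan-Meier analyses.

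**The concern.** A rate needs the same time window above and below the line. Here the numerator closes at the cut-off for every patient, while the denominator closes there only for ongoing patients. A patient who stopped shortly before the cut-off is credited with up to 70 further days that are event-free by rule, not by observation. The bias has one direction: patient-year rates are too low, and Kaplan-Meier risk sets hold patients beyond the date to which events were counted.

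Safety is the primary objective, and an interim report could go to a Health Authority or into a publication. A known mismatch in the safety rates is worth removing even if it is small.

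**Working it through.** The plan gives no figure to reproduce. It states no interim date, discontinuation share or interim follow-up, so the follow-up T (52, 78 or 104 weeks, the same for all patients) and the share s of patients who stop are assumptions. The 70 days, the 21 days and the counting rules come from SAP 2.1.4, 2.3.1, 2.4.5.1 and 3.

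**Step 1: one stopped patient.** If the last dose was d days before the cut-off, TEAE time after the cut-off is max(0, 70 − d), and treatment or efficacy time after it is max(0, 21 − d).

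- d = 5: 65 and 16 days
- d = 14: 56 and 7 days
- d = 35: 35 and 0 days
- d = 56: 14 and 0 days
- d = 70: 0 and 0 days

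**Step 2: stops spread evenly over follow-up.** Only stops in the last 10 weeks leave an excess, of 5 weeks on average. The mean excess per stopper is (10/T) × 5 = 50/T weeks. Mean TEAE time as planned is T/2 + 10 weeks for a stopper and T for an ongoing patient. The relative understatement of the rate is

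s × (50/T) / [s × (T/2 + 10) + (1 − s) × T].

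With s = 10%:

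- T = 104: 0.0481 / 99.8 = 0.05%
- T = 78: 0.0641 / 75.1 = 0.09%
- T = 52: 0.0962 / 50.4 = 0.19%

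**Step 3: completions clustered before the cut-off.** Protocol 6.2.1 ends participation when the drug becomes commercially available in the patient's country, so a cluster is possible. Assume a share s with the last injection spread evenly from 14 to 70 days before the cut-off. The mean excess is (56 + 0)/2 = 28 days = 4 weeks. The understatement is 4s / (T + 4s).

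- T = 104: 0.4/104.4 = 0.4% for s = 10%; 1.2/105.2 = 1.1% for s = 30%
- T = 52: 0.4/52.4 = 0.8% for s = 10%; 1.2/53.2 = 2.3% for s = 30%

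**Step 4: common events.** Steps 2 and 3 give every stopper the excess. Under SAP 2.4.5.1 a patient with the event leaves the denominator at the first event and adds no excess. With a constant event rate, let x = −ln(proportion event-free at the cut-off). The excess shrinks by e^(−x), and counted time falls from T to T(1 − e^(−x))/x, so to a first approximation the result is multiplied by x/(e^x − 1), which is below 1. If half the patients have had the event (assumed), x = 0.693 and the factor is 0.69, so 2.3% becomes about 1.6%. Steps 2 and 3 are therefore upper bounds under their assumptions.

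**Step 5: what does not move.** Crude adverse event percentages divide by the safety population (SAP 2.4.5.1), not by time. The final analysis has no cut-off rule.

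**The case against.** The strongest reply is that this is a negligible extension of an existing convention. The SAP credits the last dose plus 70 days whether or not follow-up was obtained, and reports insufficient follow-up separately (SAP 2.2). The larger figures need an assumed cluster of completions, and the interim is optional and descriptive. All of this is right about size. It does not remove the mismatch: in the final analysis an event in those 70 days can be counted if reported, whereas at the interim it is excluded by rule. No other section closes the gap.

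Three stronger readings are tempting, and the documents do not support them.

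- **That the interim duration rule is an error.** The formula in SAP 2.4.3.1 adds 14 days to the last injection, so an ongoing patient's duration ends two weeks after the cut-off. But the substitution is an explicit convention. With a true last injection 0 to 13 days earlier, the ordinary formula also ends 14 to 1 days after the cut-off. Injections are diary-recorded (Protocol 8.7.1) and later visits are 12 weeks apart, so at the planned lock the true date may not be in the e-CRF. What remains is an inconsistency with the statement that exposure runs to the cut-off. It touches only the exposure-duration table, because patient-year rates use TEAE length.
- **That two definitions of ongoing bias the rates.** They can differ for patients who stopped without an end-of-treatment visit, since that visit is made only where possible (Protocol 10.3.4, 10.3.5). For a stop at week 24 and a cut-off at week 104, the TEAE period would be 34 or 104 weeks depending on the reading. But the sub-bullets follow the word *Therefore*, and later bullets use completed or discontinued status, so one status-based group was evidently meant. This is an ambiguity, not a demonstrated bias.
- **That the database lock makes matters worse.** "The database is planned to be locked approximately 4 weeks after common cut-off date", so a stopped patient's TEAE period can end after the lock. Events after the cut-off are excluded whatever the lock date, so this changes no estimate.

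**Conclusion.** The truncation rule is wrong as written, and the correction is minor. Patients who completed or discontinued with a last dose less than 70 days before the cut-off contribute TEAE time in which no event can count. Interim patient-year rates are understated, and some Kaplan-Meier censoring falls after the cut-off. With 10% of patients stopping evenly, the relative understatement is at most about 0.05% (104 weeks) to 0.2% (52 weeks). With 10% to 30% completing in a cluster 14 to 70 days before the cut-off, it is at most 0.4% to 1.1% at 104 weeks and 0.8% to 2.3% at 52 weeks. These shares and follow-up times are assumptions. The direction of the bias follows from the text; its size does not. The wording on ongoing patients and on the 14 days needs clarifying, but neither is shown to be an error.

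**What to change.** In SAP section 3:

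1. Keep the rule that ongoing patients' periods end at the cut-off. Add that, for patients who completed or permanently discontinued before the cut-off, each period ends at the earlier of its usual end (SAP 2.1.4, 2.3.1) and the cut-off.
2. Use one meaning of ongoing throughout: no recorded completion or permanent discontinuation by the cut-off.
3. State whether the 14 days in SAP 2.4.3.1 are added when the cut-off stands in for the last injection. Leave the duration formula for stopped patients unchanged.

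The added rule should not be extended to all patients. Taking the earlier of the usual end and the cut-off for ongoing patients would close their treatment and efficacy periods 21 days after the last recorded injection. This would cut off patients in a temporary interruption or with injections not yet entered, which section 3 now prevents.

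The cost is a few lines of SAP text and interim programming. Discontinuation and withdrawal are already recorded in the e-CRF (Protocol 10.3.4, 10.3.5), so no new data are needed, and the final analysis does not change.

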10.1.1.17 End-of-treatment visit: Visit 17/ Week 168/ Month 40 (Day 1177± 7)

The end of study is scheduled to be in second quarter 2017 or when the drug will become commercially available for the patient in the respective country whatever comes first. Thus, the End-of-treatment visit might be performed earlier than on Week 168 according to the date of inclusion of each patient in the OLE study, or if the patient early discontinues the study.

- Collect adverse events
- Record concomitant medication
- Take vital signs including heart rate and blood pressure
- Get body weight measurement
- Physical examination
- Review patient's diet. Patient should be on a NCEP-ATPIII TLC diet or equivalent.
- Data collection on IMP administration and IMP compliance check by review of diary and treatment kit
- IVRS/IWRS contact to document the end of treatment
- Obtain fasting blood sample for:
 - Lipids: measure and/or calculation of total-C, LDL-C, HDL-C, TG, non-HDL-C, Apo B, Apo A-1, ratio Apo B/Apo A-1, and Lp (a)

- Hematology
- Chemistry
- CPK
- Liver panel
- Anti-alirocumab antibodies

- Local urine pregnancy test (females of childbearing potential only).
- Completion of EQ-5D questionnaire by patient.
- Reminders
 - For all the patients, those who prematurely discontinue the treatment irrespective of the reason and those who will complete the study, an appointment will be given for the Follow up call. This phone call will have to be scheduled 10 weeks after last injection (+/- 7 days).

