#### 2.2 DISPOSITION OF PATIENTS

This section describes patient disposition for both patient study status and the patient analysis populations. Patient study status and the patient analysis populations will be presented overall as well as separately according to treatment (placebo versus alirocumab (regardless of dose)) received in the parent study.

Screened patients are defined as any patient who met the inclusion criteria and signed the informed consent form.

Enrolled patients consist of all screened patients with a treatment kit number allocated and recorded in the IVRS/IWRS database, regardless of whether treatment kit was used or not.

For patient study status, the total number of patients in each of the following categories will be presented in the clinical study report using a flowchart diagram or summary table:

- Screened patients
- Screen failure patients and reasons for screen failure
- Enrolled patients:
  - Enrolled but not treated patients and reason for not being treated;

- Enrolled and treated patients
- Patients who did not complete the open label study treatment period as per protocol
- Patients who discontinued the open label study treatment by main reason for permanent treatment discontinuation

For the last two categories of patients percentages will be calculated using the number of treated patients in the OLE as denominator.

The incidence of premature treatment discontinuation (irrespective of the reason) and premature treatment discontinuation due to AEs will be presented graphically during OLE study, using Kaplan-Meier method.

The proportion of patients with insufficient post-treatment follow-up among those who prematurely discontinued or completed the treatment will be described.

A patient having permanently stopped or completed the IMP is considered with insufficient post-treatment follow-up or without post-treatment follow-up at the end of the study in the following cases:

- If the patient has no post-treatment OLE follow-up call/visit, unless patient died before.
- If the post-treatment OLE follow-up call/visit is less than 9 weeks after the last IMP injection in OLE.

All major deviations potentially impacting efficacy analyses, enrollment and drug-dispensing irregularities, and other important deviations will be summarized in tables giving numbers and percentages of deviations. These deviations are listed in the data review and surveillance plan.

Additionally, the following populations will be summarized.

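### At an interim analysis, the SAP's insufficient-follow-up proportion counts patients whose 10-week safety call is not yet due

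*SAP*

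**What the plan says.** SAP 2.2 defines the measure. A patient who has stopped or completed the study drug "is considered with insufficient post-treatment follow-up or without post-treatment follow-up at the end of the study" in either of two cases:

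- No call on record: "If the patient has no post-treatment OLE follow-up call/visit, unless patient died before".
- A call that was made but came too early to count: "If the post-treatment OLE follow-up call/visit is less than 9 weeks after the last IMP injection in OLE".

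SAP section 3 carries the measure to an interim. It first says who is still on treatment: "Patients without end of treatment visit performed at the time of the cut-off date will be considered as ongoing". Its last bullet then sets the population: "Analysis of proportion of patients with insufficient follow-up will be provided for patients" whose treatment had ended, whether by completion or early stopping, no later than the cut-off. No further condition is attached.

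Protocol 10.1.1.17 fixes the call: "This phone call will have to be scheduled 10 weeks after last injection (+/- 7 days"). Protocol 1.1 and 6.2.1 put the EOT visit 2 weeks after the last injection for completers, and ask for it within 5 days for patients who stop early. SAP section 4 plans the interim database lock about 4 weeks after the cut-off.

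**The concern.** The proportion is meant to show how complete the 10-week safety follow-up is, in a study whose primary objective is long-term safety. Neither criterion in SAP 2.2 separates a call that was missed from one that has not come due. At the end of the study that does no harm, because every call has fallen due. At an interim it does matter: a patient leaves ongoing status at the EOT visit, enters the denominator, and has no call on record until some weeks later. A reader of the interim report would see these patients as lapses in follow-up. SAP 1.5 says the interim option was added for Health Authority requests or scientific purposes, so the figure could reach readers outside the sponsor.

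**Working it through.** **Inputs.** All days are counted from the last injection.

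- EOT visit, completers: day 14 (Protocol 1.1, 6.2.1).
- Call: day 70, window day 63 to day 77 (Protocol 10.1.1.17).
- Earliest call that SAP 2.2 accepts: 9 x 7 = day 63, the lower edge of that window.
- Lock: about 28 days after the cut-off (SAP 4).

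**The plan's own figure.** The protocol summary puts the call 8 weeks after the EOT visit. Check: 70 - 14 = 56 days = 8 weeks, and Week 168 + 8 = Week 176, as in the flow chart. It reproduces.

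**Span in which a per-protocol completer is scored as insufficient.**

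- Call on the first permitted day: 63 - 14 = 49 days = 7 weeks.
- Call on the last permitted day: 77 - 14 = 63 days = 9 weeks.
- If calls up to lock count, subtract 4 weeks: 3 to 5 weeks.
- Early discontinuer seen on day 5: 63 - 5 = 58 to 77 - 5 = 72 days, about 8.3 to 10.3 weeks.

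**One patient.** A completer has the last injection 35 days before the cut-off and an EOT visit on day 14. The call window opens 63 - 35 = 28 days after the cut-off and closes 77 - 35 = 42 days after it. At the cut-off this patient is no longer ongoing, is in the denominator, and has no call. The first criterion is met although nothing has been missed.

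**Illustrative share of exits affected.** Assume EOT visits are spread evenly over the T weeks before the cut-off and every call is made on time. The falsely scored share runs from 7/T to 9/T, or from 3/T to 5/T if calls up to lock count.

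| T (weeks) | Calls to cut-off only | Calls to lock counted |
|---|---|---|
| 26 | 26.9-34.6% | 11.5-19.2% |
| 52 | 13.5-17.3% | 5.8-9.6% |
| 104 | 6.7-8.7% | 2.9-4.8% |

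If last injections rather than EOT visits are spread evenly over T weeks, the share is 49/(7T - 14) to 63/(7T - 14). That gives 29.2-37.5%, 14.0-18.0% and 6.9-8.8% without the lock allowance, so the choice matters little.

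**Effect on the reported figure (invented counts).** Take 100 exited patients, 30 with the call not yet due, and 4 of the other 70 truly lacking adequate follow-up. As written: (4 + 30)/100 = 34%. Among patients whose call was due: 4/70 = 5.7%.

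**The case against.** The best defence is textual. SAP 2.2 speaks of status at the end of the study, and Protocol 6.2.1 makes a patient's end of study the last planned call. A patient 5 weeks after the last dose has not got there. SAP section 3 also applies the rules of other sections only where they are applicable. A programmer could therefore leave out patients whose call is not due. That reading is open, but section 3 does not adopt it: for this one analysis it names its own population, and that population is everyone who has exited. Leaving patients out would need a rule that the SAP does not contain.

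The second defence is the lock. Section 3 drops later adverse events ("AEs occurring, worsening or becoming serious after the cut-off date will not be included in the analyses") as well as later medications, exits and deaths, but does not mention calls. If calls up to lock count, the span shrinks to 3 to 5 weeks. This stands as a limit on size; it does not remove the problem.

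The third is weight. Interims are optional, no test is involved, and the final analysis follows the last patient's last visit, when every call has been due. All of that stands and makes the point minor.

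**Conclusion.** The point holds as a minor one. Read as written, the interim rule scores per-protocol completers as insufficient for about 7 to 9 weeks after the EOT visit, or 3 to 5 weeks if calls up to lock count. The spans follow from the documents. The percentages do not: they rest on an assumed even spread of exits and on every call being on time, and the plan gives no exit pattern. The final analysis and the TEAE tables are unaffected.

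A reader might infer two stronger claims, and the documents support neither.

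- *Post-treatment adverse event percentages are diluted in the same way.* Section 3 does say that analyses "of post-treatment AEs, post-study deaths and post-treatment medications will be performed" on all exited patients. But the post-treatment period opens on day 71 (SAP 2.1.4) and the study ends at the call, due by day 77, so even a fully followed patient contributes only about 0 to 7 days. Those percentages will be low at the final analysis too. The only adverse event denominator stated is the safety population (SAP 2.4.5.1).
- *The figure could approach 100% in a country where the drug has just been launched.* SAP 2.2 presents disposition overall and by parent-study treatment. No by-country table is planned. Exits may cluster after a launch, but the documents do not show by how much.

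**What to change.** Amend the last bullet of SAP section 3:

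- Compute the interim proportion among patients whose last injection was at least 77 days (70 + 7) before the cut-off, with the SAP 2.2 criteria unchanged.
- Show the remaining completed or discontinued patients in separate rows: call already done (sufficient, or under 9 weeks), died before the call, or follow-up call not yet due.
- State whether calls made between the cut-off and the lock count.

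The separate rows are needed because a bare 77-day cut would label a call already made on days 63 to 76 as not yet due, and would hide a call made before week 9.

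Leave the post-treatment adverse event, medication and post-study death summaries as they are. Under SAP 2.1.4 and 2.1.4.2 the post-study period begins after the call once it is done. With a call on day 63, a death on day 66 and a cut-off on day 68, the death is post-study; limiting the table to patients more than 70 days from the last dose would lose it.

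Cost: a few lines of SAP text, one derived flag, and a smaller interim denominator.
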